7.4.1. Information of institution

The following will be recorded in the CRF for each patient:

- CRF number (Patient number): The investigator will sequentially assign each patient a patient identification number, which will be a 4-digit number. It will be combined with code number of institution by sponsor.
- Name of institution
- Name of department
- Name of investigator
- Date of signing data privacy statement
- Signature of investigator: Contracted investigator must sign after identifying the CRF.

7.4.2. Patient information (Baseline)

The following will be recorded in the CRF for each patient:

- Inclusion criteria: Subjects can be enrolled with satisfying all inclusion criteria.
- Exclusion criteria: Subjects cannot be enrolled with meeting any of exclusion criteria.
- Age
- Sex
- Pregnancy: If 'yes', then record the week of pregnancy.
- Breast-feeding
- Diagnosis
- Diagnosis date
- Severity of the disease

7.4.3. Medical history

Select among 'yes' or 'no' for medical history of followings. Past or present disease (including hepatic and renal impairment) will be determined based on the first PRISTIQ®

administration date. Record adequate full name of the disease down as the Medical Terminology Dictionary indicates (written by Korean Medical Society).

7.4.3.1. Renal disorder / Hepatic disorder

If 'yes', record the name of the disease, severity and status.

7.4.3.2. Allergic history

If 'yes', record the allergen and status.

7.4.3.3. Other diseases / symptoms

If 'yes', record the name of the disease and status.

7.4.4. Recent past psychotropic medication

Select among 'yes' or 'no' for past psychotropic medications which were terminated within 30 days before the first administration of PRISTIQ®. The following will be recorded in the CRF for each patient:

- Name of medication
- Route of administration
- Treatment start date
- Treatment stop date

7.4.5. Administration status for PRISTIQ®

Record the followings with regard to administration status for the study drug. If the posology is changed (including wash-out), please record in a separate row and the reason.

- Treatment start date
- Treatment stop date
- Daily dosage and frequency
- Reason for dose adjustment: Select one among 'planned dose increase or decrease', 'cure or improvement', 'occurrence of adverse event', 'withdrawal due to lack of efficacy' or 'other'. If 'other', record the specific reason.

7.4.6. Concomitant medications

Record the medicated drug while PRISTIQ® is being administrated. First select either 'yes' or 'no' then record in more details if selected 'yes'.

- Name of medication (generic name)

- Treatment start date
- Treatment stop date
- Ongoing: If the treatment is not terminated until the timing of CRF completion, check 'ongoing'.
- Purpose of treatment: Select one among 'treatment for major depressive disorder', 'treatment for other diseases', 'treatment for an adverse event', 'prevention of drug side effect', or 'other'. If 'other', record the specific reason.

7.4.7. Blood Pressure

If the physician performed blood pressure check for diagnostics or monitoring in usual medical practice, check 'done' and record the results. If there is any clinically significant abnormal result in blood pressure during or after administration compared to one before administration, please check 'yes' and record the abnormality in "9. Safety evaluation" clause.

- Date of blood pressure check (before / during / after)
- Results (sBP / dBp)

7.4.8. Clinical laboratory

If the physician performed laboratory test for diagnostics or monitoring in usual medical practice, check 'done' and record the results. If there are any clinically significant abnormality in laboratory test results during or after administration compared to one before administration, please check 'yes' and record the abnormality in "9. Safety evaluation" clause.

- Laboratory test item
- Normal range (unit)
- Date of laboratory test
- Test results (before / during / after)

7.4.9. Effectiveness Evaluation

7.4.9.1. CGI-I scale (Clinical Global Impression – Improvement scale)

Clinical effectiveness will be evaluated after 8 weeks treatment (within 2 weeks of the last administration) using CGI-I scale as follows. In case of long-term use study subject, the result will be also assessed after 6 months treatment of PRISTIQ® (within 2 weeks of the last administration).

- 1. Very much improved

- 2. Much improved
- 3. Minimally improved
- 4. No change
- 5. Minimally worse
- 6. Much worse
- 7. Very much worse

7.4.9.2. Final effectiveness evaluation

Final effectiveness will be evaluated at completing the administration of PRISTIQ® or at around 8 weeks treatment if PRISTIQ® has been still administered. In case of long-term use study subject, the result will be assessed after 6 months treatment of PRISTIQ®. Final effectiveness will be evaluated as ‘improved’, ‘no change’, ‘worse’ or ‘unevaluable’ based on overall patient’s clinical response, CGI-I scale and investigator’s judgment.

- Improved: In the case of judgment that there is the improvement of symptoms related to MDD.
- No change: In the case that there is no significant change compared to patient’s status before PRISTIQ® administration.
- Worse: In the case that symptoms are getting worse compared to patient’s status before PRISTIQ® administration.
- Unevaluable: In the case that the medical charts do not have adequate progress notes to make a judgment on clinical response.

7.4.10. Safety Evaluation

Safety will be assessed based on adverse events reported for all patients who received at least one dose of PRISTIQ® and completed safety follow-up. Any adverse events will be recorded in the CRF including the information of the specific conditions or events, duration of the event persisted, seriousness, severity, causal relationship to PRISTIQ®, actions taken, and outcome.

7.4.10.1. Definition of adverse events

An AE is any untoward medical occurrence in a patient administered a medicinal product. The event need not necessarily have a causal relationship with the product treatment or usage. Examples of adverse events include but are not limited to:

- Abnormal test findings (see below for circumstances in which an abnormal test finding constitutes an AE);

- Clinically significant symptoms and signs;
- Changes in physical examination findings;
- Hypersensitivity;
- Progression/worsening of underlying disease;
- Lack of efficacy;
- Drug abuse;
- Drug dependency.

Additionally, for medicinal products, they may include the signs or symptoms resulting from:

- Drug overdose;
- Drug withdrawal;
- Drug misuse;
- Off-label use;
- Drug interactions;
- Extravasation;
- Exposure during pregnancy;
- Exposure during breast feeding;
- Medication error;
- Occupational exposure.

Abnormal test findings

The criteria for determining whether an abnormal objective test finding should be reported as an adverse event are as follows:

- Test result is associated with accompanying symptoms, and/or
- Test result requires additional diagnostic testing or medical/surgical intervention, and/or

- Test result leads to a change in study dosing or discontinuation from the study, significant additional concomitant drug treatment, or other therapy, and/or
- Test result is considered to be an adverse event by the investigator or sponsor.

Merely repeating an abnormal test, in the absence of any of the above conditions, does not constitute an adverse event. Any abnormal test result that is determined to be an error does not require reporting as an adverse event.

7.4.10.2. Definition of serious adverse events (SAEs)

A serious adverse event is any untoward medical occurrence in a patient administered a medicinal or nutritional product (including pediatric formulas) at any dose that:

- Results in death;
- Is life-threatening;
- Requires inpatient hospitalization or prolongation of hospitalization (see below for circumstances that do not constitute adverse events);
- Results in persistent or significant disability/incapacity (substantial disruption of the ability to conduct normal life functions);
- Results in congenital anomaly/birth defect.
- Is important medical event (if it is determined that the event may jeopardize the subject or may require intervention to prevent one of the other outcomes listed in the definition above)

Medical and scientific judgment is exercised in determining whether an event is an important medical event. An important medical event may not be immediately life-threatening and/or result in death or hospitalization. However, if it is determined that the event may jeopardize the patient or may require intervention to prevent one of the other outcomes listed in the definition above, the important medical event should be reported as serious.

Examples of such events are intensive treatment in an emergency room or at home for allergic bronchospasm; blood dyscrasias or convulsions that do not result in hospitalization; or development of drug dependency or drug abuse.

Additionally, any suspected transmission via a Pfizer product of an infectious agent, pathogenic or non-pathogenic, is considered serious. The event may be suspected from clinical symptoms or laboratory findings indicating an infection in a patient exposed to a Pfizer product. The terms “suspected transmission” and “transmission” are considered synonymous. These cases are considered unexpected and handled as serious expedited cases by PV personnel. Such cases are also considered for reporting as product defects, if appropriate.

Hospitalization

Hospitalization is defined as any initial admission (even if less than 24 hours) to a hospital or equivalent healthcare facility or any prolongation to an existing admission. Admission also includes transfer within the hospital to an acute/intensive care unit (e.g., from the psychiatric wing to a medical floor, medical floor to a coronary care unit, neurological floor to a tuberculosis unit). An emergency room visit does not necessarily constitute a hospitalization; however, an event leading to an emergency room visit should be assessed for medical importance.

Hospitalization in the absence of a medical AE is not in itself an AE and is not reportable. For example, the following reports of hospitalization without a medical AE are not to be reported:

- Social admission (e.g., patient has no place to sleep)
- Administrative admission (e.g., for yearly exam)
- Optional admission not associated with a precipitating medical AE (e.g., for elective cosmetic surgery)
- Hospitalization for observation without a medical AE
- Admission for treatment of a pre-existing condition not associated with the development of a new AE or with a worsening of the pre-existing condition (e.g., for work-up of persistent pre-treatment lab abnormality)
- Protocol-specified admission during clinical study (e.g., for a procedure required by the study protocol)

7.4.10.3. Adverse events data collection

The investigator collects data on safety events as specified in Section 9 including all adverse events that occur during the observation period regardless of causal relationship to PRISTIQ®. The information on adverse events should include the specific conditions or events, duration of the events (start date and stop date), seriousness (serious or non-serious), severity, causal relationship to PRISTIQ®, actions taken, and outcome.

Check either 'yes' or 'no' in adverse event occurrence section. If 'yes', record in detail.

- Adverse event: Record the term of adverse event. If possible, specify diagnosis, not individual symptoms.
- Date of onset: Record the date of onset.
- Severity: Severity evaluation of adverse events must be done according to the following category.

1. Mild- Not causing any significant problem to the subject; Continuous medication of study drug is possible without dose adjustment.
2. Moderate- Cause a problem that does not interfere significantly with usual activities or the clinical status; Dose adjustment of study drug or other therapy is needed due to adverse event.
3. Severe- Cause a problem that interferes significantly with usual activities or the clinical status; Study drug should be stopped due to adverse event.

If the severity of an adverse event changed, the adverse event must be entered separately. Record stop date of previous severity and onset date of new severity – along with completion of all other items.

- Action: Check all relevant actions.

1) PRISTIQ®: Check the appropriate number for the adjustment of PRISTIQ® resulted from the adverse event.

1. Withdrawn (temporarily or permanently, or delayed)
2. Dose reduced
3. Dose increased
4. Dose not changed
5. Unknown
6. Not applicable

2) Others: After the onset of adverse event, the investigator should indicate other actions taken and record in detail.

1. Treatment given (please specify in concomitant medication section)
2. Others (please specify)
3. No action taken

- Seriousness: Check either ‘yes’ or ‘no’ for the question, ‘Is this case under the criteria of serious adverse event?’ If ‘yes’, record the appropriate number for the category of seriousness.

A serious adverse event is any untoward medical occurrence at any dose that:

- results in death;

- is life-threatening;
- requires inpatient hospitalization or prolongation of hospitalization;
- results in persistent or significant disability/incapacity (substantial disruption of the ability to conduct normal life functions);
- results in congenital anomaly/birth defect.
- Is important medical event (if it is determined that the event may jeopardize the subject or may require intervention to prevent one of the other outcomes listed in the definition above)

Medical and scientific judgment is exercised in determining whether an event is an important medical event. An important medical event may not be immediately life-threatening and/or result in death or hospitalization. However, if it is determined that the event may jeopardize the subject or may require intervention to prevent one of the other outcomes listed in the definition above, the important medical event should be reported as serious.

Examples of such events are intensive treatment in an emergency room or at home for allergic bronchospasm; blood dyscrasias or convulsions that do not result in hospitalization; or development of drug dependency or drug abuse.

Record the followings at the end of the study or after the resolution of adverse event.

- Outcome: Select among ‘yes’, ‘unknown’, or ‘no-resolved’ as a reply to a question, ‘Is the adverse event still present?’ If ‘no-resolved’, record the resolved date.
- Causality of adverse event to the study drug: The causal relationship of adverse event to the study drug must be allocated by the psychiatrist according to the following criteria.

(1) Certain

- It follows a reasonable time sequence from administration of the drug (before and after the study medication).
- It could not be explained by other drugs, chemical substance or accompanying diseases.
- It has clinically reasonable reaction on cessation of the drug.
- It has pharmacological or phenomenological reaction to re-administration of the drug, where necessary.

(2) Probable/likely

- It follows a reasonable time sequence from administration of the drug (before and after the study medication).
- It could not be explained by other drugs, chemical substance or accompanying diseases.
- It has clinically reasonable reaction on cessation of the drug (No information on re-administration).

(3) Possible

- It follows a reasonable time sequence from administration of the drug.
- It could also be explained by other drugs, chemical substance or accompanying diseases.
- It lacks information or has unclear information on discontinuation of the drug.

(4) Unlikely

- It is not likely to have a reasonable causal relationship from administration of the drug. Rather, it seems to be temporary.
- It could also be reasonably explained by other drugs, chemical substances or latent diseases.

* Other causality of adverse event: If the adverse event is not related to the study drug, psychiatrists should indicate the most appropriate cause from the followings and record in detail.

1. Disease under the study
2. Other disease (please specify)
3. Concomitant treatment –drug or non-drug (please specify)
4. Others (please specify)

(5) Conditional/unclassified

- It needs more data to make an appropriate assessment or its additional data are being reviewed.

(6) Unaccessible/unclassifiable

- Lack of sufficient information or conflicting information hampers accurate causality assessment or supplementation or confirmation.

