8.2.1.4 Adverse Events by Preferred Terms (AEs/ADRs/SAEs)

All AEs recorded in CRFs will be classified into the system organ class (SOC) and the terms of AE will be coded according to the classification of AEs in 'WHO-ART'. All AEs, except for 'Unlikely', will be considered as AE whose causal relationship to study drug cannot be excluded (hereinafter "Adverse Drug Reaction (ADR)").

- The number and percentage of AE will be presented overall and by preferred term. This will be repeated by:
 - severity
 - action
 - other action
 - seriousness
 - outcome
 - causality of adverse event to the study drug
 - other causality of adverse event to the study drug
- The number of subjects and the number of unexpected AE/ADR, Serious AE (SAE)/Serious ADR (SADR), unexpected SAE/SADR, AE/ADR will be calculated according to the preferred terms. Also, the proportion of subjects to whom AE occurred will be estimated.
- The subjects with Serious AE, unexpected AE, unexpected serious AE, AE of Geriatric, pregnant, breast-feeding, renal disorder, hepatic disorder and long term subjects will be listed for safety analyses sets.
- For subjects excluded from safety analysis set*, the number of subjects and the number of unexpected AE/ADR, Serious AE(SAE)/Serious ADR (SADR), unexpected SAE/SADR, AE/ADR will be calculated according to the preferred terms. Also, the proportion of subjects to whom AE occurred will be estimated.

* Subjects who enrolled for duplication or Subjects who have not taken PRISTIQ® or Subjects for whom adverse event status could not be established (Adverse Events status is unknown or missing in the CRF) will be excluded from this analysis.

Note: Unexpected AEs/ADRs will be classified by medical review and with reference to the local product document. Terms already included in the local product document are classified as 'expected'. All other terms that are not included in the local product document will be classified as 'unexpected'. These can't be classified without the local product document.

- For subjects excluded from safety analysis set, Serious AE, unexpected AE, unexpected serious AE will be listed for subjects excluded from safety analysis set.

- In re-examination report, SAE/SADR and unexpected AE/unexpected ADR in accordance with PT will be presented respectively according to the frequency categories of adverse events in the approved local label.

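### Each adverse event severity grade joins impact on the patient to a judgement about treatment, with no rule for when the two disagree

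*Protocol*

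**What the plan says.** Protocol 7.4.10.3 makes the scale compulsory: "Severity evaluation of adverse events must be done according to the following category". There are three grades and no option for an event that cannot be graded.

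- Mild: "Mild- Not causing any significant problem to the subject; Continuous medication of study drug is possible without dose adjustment".
- Moderate grade: "Cause a problem that does not interfere significantly with usual activities or the clinical status; Dose adjustment of study drug or other therapy is needed".
- Severe: "Severe- Cause a problem that interferes significantly with usual activities or the clinical status; Study drug should be stopped due to adverse event".

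The same section has a separate Action item for the study drug, with the instruction "Check the appropriate number for the adjustment of PRISTIQ® resulted from the adverse event". It offers six options, including unknown and not applicable. A further item records other actions (treatment given, others, none). If severity changes, the event is entered again as a separate record with its own dates.

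SAP 8.2.1.4 states "The number and percentage of AE will be presented overall and by preferred term", and repeats this by severity, by action and by other action, among other splits. Neither document ranks the two clauses of a grade, and the SAP gives no rule for recombining records split by a severity change.

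**The concern.** How much an event affects the patient and what it implies for treatment are different questions, and one grade is asked to answer both. They need not agree:

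- Events are collected whatever their cause. One unrelated to the drug can interfere significantly with usual activities while dosing can continue unchanged. It meets the impact clause of Severe and the drug clause of Mild, and no grade in full.
- Protocol 7.1 requires at least 28 days of observation after the last dose when treatment stops before week 8. For an event that begins in that period, a clause about adjusting or stopping the drug has no clear meaning. The Action item allows for this with its not-applicable option; the severity scale does not.

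Two investigators could then grade the same event differently, and the severity split would mix impact with treatment judgement. A change in the need for drug adjustment or other therapy, with no clinical change, could also be read as a severity change. It would then create another row in the number of AEs reported under SAP 8.2.1.2 to 8.2.1.4.

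**Working it through.** The documents give no figure on this point, so there is none to reproduce. The check counts combinations.

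**Inputs (Protocol 7.4.10.3).** Impact has three levels: no significant problem; a problem without significant interference; significant interference. Treatment judgement has three levels: can continue unchanged; dose adjustment or other therapy needed; drug should be stopped.

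**Step 1: main grid.** Number of combinations = 3 × 3 = 9. A cell has a full match if both clauses of one grade hold.

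| Impact | Continue unchanged | Adjustment or other therapy | Stop |
|---|---|---|---|
| No significant problem | Mild | none | none |
| No significant interference | none | Moderate | none |
| Significant interference | none | none | Severe |

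Full matches: 3 of 9. No full match: 6 of 9 = 67%. If one clause were enough, each of those 6 cells would point to two grades. On either reading, 6 cells lack a single grade.

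**Step 2: finer grid.** Here the recorded action stands in for the judgement, which is an approximation. With four known drug actions (withdrawn, reduced, increased, unchanged) and other therapy yes or no, there are 3 × 4 × 2 = 24 cells.

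- No significant problem: Mild needs the drug unchanged, giving 2 cells.
- No significant interference: Moderate needs a dose change (2 × 2 = 4 cells) or other therapy with the drug unchanged or withdrawn (2 cells), giving 6 cells.
- Significant interference: Severe needs withdrawal, giving 2 cells.

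Full matches: 2 + 6 + 2 = 10. No full match: 24 − 10 = 14 (58%). Adding the unknown and not-applicable actions gives 3 × 6 × 2 = 36 cells and 2 + 8 + 2 = 12 full matches, leaving 24 (67%).

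**Step 3: overlap of Mild and Moderate.** A complaint that causes no significant problem also does not interfere significantly, so it can satisfy both impact clauses. On that reading, cells with no full match or with two fall to 10 of 24 (42%) or 18 of 36 (50%). One cell then meets Mild and Moderate in full: no significant problem, drug unchanged, other therapy given. A slight headache that needs an analgesic is an example.

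**Step 4: effect on counts.** If k severity-change rows arise from treatment need alone, N events are reported as N + k. The documents give no basis for k.

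**Step 5: after the fix.** If the grade depends on impact alone and the three levels do not overlap, each row of the main grid has one grade, so 9 of 9 cells have exactly one.

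**The case against.** The strongest reply has four parts.

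**The second clauses are judgements, not actions.** They say what is possible, needed or ought to happen, while the Action item records what followed. This stands. A reader might infer that the severity table simply duplicates the action table, or that any minor event after which the drug was stopped becomes Severe. The wording supports neither: that a drug was stopped does not show that the event required it. The tables overlap but are not the same.

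**The 67% is a property of the grid.** Any 3 × 3 grid has 6 off-diagonal cells, and impact and treatment judgement are probably correlated. This stands too. A reader might infer that two-thirds of events, or some other sizeable fraction, are misgraded; the documents give no event frequencies to support that.

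**Removing the second clauses alone would leave Mild and Moderate without a boundary.** Correct: the therapy clause is now the main thing separating them, so the impact wording must change as well.

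**Little depends on severity, and it is late.** The safety endpoint is occurrence of an adverse event (SAP 6.1), and there are no hypotheses (SAP 4). Planned data collection ended on 01 Dec 2018 (Protocol 4), and SAP version 4.0 is dated 08-NOV-2019. Protocol 7.9 also says that regulation determines the protocol; whether that extends to this scale cannot be checked here. These facts limit the consequence and mean that, if the planned dates held, new wording reaches no further records. They do not supply the missing rule, and the analysis changes below need only collected data.

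**Conclusion.** The concern holds in a limited form. The scale is compulsory, each grade has two clauses that can disagree, and no rule settles the disagreement. Only 3 of 9 combinations meet both clauses of one grade. The share without a single full match is 58% to 67% on the finer grids, or 42% to 50% if the Mild and Moderate impact clauses are read as overlapping. All of these are shares of possible combinations; the share of events is unknown.

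The effect reaches the severity split in SAP 8.2.1.4 and possibly the event counts. A reader might infer that the main safety results are compromised, but the documents do not support that. Subject-level incidence with its confidence interval and the baseline-factor tests use the occurrence of an event, and seriousness and causality are assessed separately from the grade.

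The conclusion assumes that no rule for discordant cases exists outside these two documents, for example in CRF completion instructions.

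**What to change.** **Protocol 7.4.10.3 and CRF instructions.** Define severity only by effect on usual activities or clinical status, with levels that do not overlap: for example no interference, some but not significant interference, and significant interference. Leave drug and therapy consequences to the existing Action items, so no information is lost. The severity and action passages must be reconciled; no view is taken here on when the drug should be adjusted or stopped.

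**SAP 8.2.1.4, for records already collected.** Add a cross-table of severity by action on PRISTIQ and by other action. It shows how far the recorded grades follow what was done, with a note that action taken is only a proxy for the judgement in the grade. State that an event split only by a severity change counts as one event at its worst grade. The protocol requires the stop date of the old severity and the onset date of the new one, so such rows can be linked by subject, term and dates.

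**Cost.** One wording change, one cross-table and one counting rule, with no new data. Grades recorded before and after the change would not be directly comparable without the cross-table. Querying sites about discordant records is optional and not needed for the fix.

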8.1.2 Analysis for Categorical Data

Descriptive statistics for categorical variables will be given as frequencies and percentages. The denominator will be the number of subjects included either in the safety analysis set or effectiveness analysis set depending on where the analysis is presented. But in case of pregnancy and breast-feeding analysis, subjects who collected “Not Applicable (male)” are excluded from the denominator and footnote will be added to the relevant outputs to indicate the number of subjects collected “Not Applicable (male)”. Likewise, in analysis of severity of disease, subjects who collected “Unknown” are excluded from the denominator and footnote will be added to the relevant outputs to indicate the number of subjects collected “Unknown”.

Where appropriate, the percentages will be presented with a corresponding 95% confidence interval. Comparisons between subcategories of each baseline characteristic will be made using chi-square test or Fisher’s exact test. Test statistics include p-value. When more than 20% of expected frequency of the cell count is less than 5, Fisher’s exact test should be used instead of chi-square test.

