8.2.1.2 Adverse Events

All adverse events reported after start of administration of PRISTIQ® will be considered as on-treatment and summarised. Adverse events reported with partial dates of onset will be assumed as on-treatment, unless month/year of AE onset date is before start date of PRISTIQ®.

In the safety analysis set, the number of subjects to whom AE occurred and the number of AEs will be calculated and the incidence rate of AEs will be estimated with its 95% confidence interval.

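### An adverse event that changes severity is entered again in full, and the SAP has no rule to link the entries, so event-level tables can count one event more than once

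*Protocol*

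**What the plan says.** **Data entry.** Protocol 7.4.10.3 instructs: "If the severity of an adverse event changed, the adverse event must be entered separately". It continues: "Record stop date of previous severity and onset date of new severity – along with completion of all other items". The other items in that section are action, seriousness, outcome and causality. Outcome is answered at study end or once the event has resolved, and asks whether the event is ongoing. "If ‘no-resolved’, record the resolved date".

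**Tabulation.** In the safety analysis set, SAP 8.2.1.2 states that "the number of subjects to whom AE occurred and the number of AEs will be calculated". SAP 8.2.1.3 repeats both counts by baseline characteristic. SAP 8.2.1.4 states: "The number and percentage of AE will be presented overall and by preferred term". It repeats this by severity, action, other action, seriousness, outcome, causality and other cause. It also asks for numbers of subjects and numbers of events, by preferred term, for AEs, ADRs, SAEs, serious ADRs and unexpected events.

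**Denominator.** SAP 8.1.2, on categorical data: "The denominator will be the number of subjects included either in the safety analysis set or effectiveness analysis set".

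**Where a linking rule might be expected.** Protocol 7.6 (data management) covers double entry, queries and coding. SAP section 7 (missing values) is marked not applicable. SAP Appendix 1 covers software and ambiguous values. None of them mentions entries split by severity.

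**The concern.** The entry rule turns one clinical event into two or more complete records by design. The SAP asks for counts of events without defining the unit, so a programmer who tabulates the AE records as they stand will count some events repeatedly.

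Splitting need not be rare. Protocol 7.4.10.3 defines the severity grades partly by what happens to study drug (no adjustment, adjustment or other therapy, stopping). An event whose management changes can therefore change grade and be split. The extra entries would then come disproportionately from such events, which could alter the make-up of the event-level tables as well as their totals.

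Serious and unexpected events come first in the study objectives (Protocol section 6), and the counts go into the periodic and final reports to the regulator. Without a rule, two programmers could report different event counts from the same database.

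**Working it through.** The plan contains no figure to reproduce: no expected number of AEs and no expected rate of severity change. The check sets the two texts side by side and then does simple arithmetic on assumed inputs.

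**1. Which counts are exposed if entries are tabulated as they stand**

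| Output | Can one event count more than once? |
|---|---|
| Number of AEs (SAP 8.2.1.2, 8.2.1.3) | Yes, once per entry |
| AEs by action, seriousness, outcome, causality (8.2.1.4) | Yes, once per entry |
| Number of unexpected AEs | Yes; the status follows the term, so every entry carries it |
| Number of ADRs | Yes, for each entry not rated unlikely |
| Number of SAEs | Only if more than one entry is marked serious |
| Number and proportion of subjects, with CIs and tests (8.2.1.3) | No |

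The incidence rate in SAP 8.2.1.2 has no stated numerator. It is unaffected if it means subjects with an AE, and exposed only if it is read as event-based.

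**2. Size of the event count**

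Entries = E × (1 + c × k), where E is the number of distinct events, c the share that change severity, and k the number of changes in each of those events. Assume E = 200.

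| c | k = 1 | k = 2 |
|---|---|---|
| 5% | 200 × 1.05 = 210 | 200 × 1.10 = 220 |
| 10% | 200 × 1.10 = 220 | 200 × 1.20 = 240 |
| 20% | 200 × 1.20 = 240 | 200 × 1.40 = 280 |

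The overcount is c × k: 5% to 20% with one change per event, 10% to 40% with two.

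**3. SAEs**

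Assume 10 SAEs, of which 3 change severity once. If both entries of those 3 are marked serious, the count is 10 + 3 = 13. If only one entry of each is, it stays at 10.

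**4. Denominator**

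SAP 8.1.2 points to subjects, while 8.2.1.4 asks for a percentage of AEs. If entries were divided by an assumed 600 subjects (the planned enrolment), the true 200/600 = 33.3% would show as 210/600 = 35.0%, 220/600 = 36.7% or 240/600 = 40.0%. Neither section says which denominator applies to event percentages.

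**5. Subject level**

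Assume 120 of 600 subjects have at least one AE. The proportion is 20.0% (exact 95% CI 16.9% to 23.4%) for every value of c and k, because a subject counts once however many entries there are.

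**The case against.** **The SAP never says that it counts entries.** This stands. It speaks of AEs, and Protocol 7.4.10.3 itself treats the split record as one adverse event with more than one entry. Counting each event once is compatible with the text. The defect is therefore an undefined counting unit. It still needs repair, because nothing tells the programmer to join the entries or which entry's attributes represent the event.

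**The outcome table.** A reader might infer a bias towards resolved, because the earlier entry is closed with a stop date. The documents do not support this. The outcome item asks about the event, not the severity segment, and is completed at study end or after resolution. The stop date of a severity grade is also distinct from the resolved date. If every entry carries the event's final outcome and severity change is unrelated to resolution, an assumed 60% resolved stays at 60%: 126/210, 132/220, 144/240. If the two are related, the share could move either way. A systematic rise would need sites to record closed segments as resolved, which the protocol does not ask for.

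**The severity table.** Showing each grade separately may be intended there, so it would be wrong to call every event-level table in 8.2.1.4 erroneous.

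**The consequence is descriptive.** This also stands. The subgroup comparisons of AE occurrence use proportions of subjects, and SAP section 4 sets no hypothesis or decision rule.

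**The CRF is not among the documents.** It may hold a field linking split entries. If it does, the derivation is easier, but the SAP still has to call for it.

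**Conclusion.** The concern holds as an unspecified counting rule. The protocol requires a separate full entry when severity changes, and neither document links such entries, so the plan run as written can count one event more than once in event totals and in the action, seriousness, outcome and causality tables.

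The size depends on the share of events that change severity, which the documents do not give. For 200 assumed events, 5% to 20% changing once gives 210 to 240 entries. Doubling of an SAE is conditional on more than one entry being marked serious; a non-serious event that worsens to serious can still yield a single serious entry. Subject-level results stand as planned, and no direction of error in the outcome table is claimed. The change should be made because it is cheap and the event counts are reported to the regulator.

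**What to change.** Add to SAP 8.2.1.2 and 8.2.1.4:

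- **Linking.** Consecutive entries of the same term in the same subject, where the stop date of the previous severity meets the onset date of the new one, form one event. State whether meeting means the same day or the next day.
- **Counting.** Each linked event is counted once.
- **Attributes.** Use maximum severity; serious if any entry is serious; outcome from the last entry; the strongest recorded causality; and all actions taken across entries. Give the causality order explicitly, including the two undetermined categories, so that any entry not rated unlikely makes the event an ADR, in line with 8.2.1.4.
- **Listings.** Keep the split entries there, with their dates and severities.
- **Denominators.** Use the number of events for event percentages and the number of subjects for subject percentages. Name the numerator of the incidence rate in 8.2.1.2.

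The cost is SAP wording and one short derivation step, with no new data. The small downside is that summary tables will no longer show severity changes within an event; these remain in the listings.
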